Isotopic bone scans may be used as a method of assessment to identify the presence of new bone lesions at follow-up visits. NLs may be recorded in case positive hot-spots appear on a bone scan that were not present on a previous bone scan; however, a newly observed equivocal hot-spot on a bone scan which cannot be verified with correlative imaging (CT, MRI, X-ray) of the same anatomical region shall not be the only trigger for a PD assessment at that timepoint.

FDG-PET/CT scan

¹⁸F-Fluoro-deoxyglucose positron emission tomography/computed tomography (FDG-PET/CT) scans may be used as a method for identifying NLs, according to the following algorithm: NLs will be recorded where there is positive ¹⁸F-Fluoro-deoxyglucose uptake³ not present on baseline or prior FDG-PET scan or in a location corresponding to a new lesion on CT/MRI at the same follow-up visit. If there is no baseline or prior FDG-PET scan available, and no evidence of NLs on CT/MRI scans then follow-up CT/MRI assessments should be continued, scheduled as per protocol or clinical indicated, in order to verify NLs.

At present, low dose or attenuation correction CT portions of a combined FDG-PET/CT scan are of limited use in anatomically-based efficacy assessments, and it is therefore suggested that they should not substitute for dedicated diagnostic contrast-enhanced CT scans for tumour measurements by RECIST 1.1. In exceptional situations, if a study site can document that the CT performed, as part of a PET/CT examination, is of identical diagnostic quality (with IV contrast) to a dedicated diagnostic CT scan, then the CT portion of the PET/CT can be used for RECIST 1.1 tumour assessments. Caution that this is not recommended because the PET portion of the CT introduces additional (PET) data that may bias an Investigator if it is not routinely or serially performed.

³ A positive FDG-PET scan lesion should be reported only when an uptake (eg, SUV) greater than twice that of the surrounding tissue or liver is observed.

Tumour response evaluation

Schedule of evaluation

The methods of assessment of tumour burden used at baseline CT/MRI scans of the chest and abdomen (including the entire liver and both adrenal glands) must be used at each subsequent follow-up assessment. Additional imaging may be performed based on the signs and symptoms of the patient, eg, NLs at follow-up.

Baseline assessments should be performed no more than 28 days before the date of first IP administration, and ideally should be performed as close as possible to the date of first IP administration. Efficacy by RECIST 1.1 for all patients will be assessed according to the schedules of assessment. If an unscheduled assessment is performed, and the patient has not progressed, every attempt should be made to perform the subsequent assessments at their scheduled imaging visits.

Target lesions

Documentation of target lesions

A maximum of 5 measurable lesions, with a maximum of 2 lesions per organ (including lymph nodes collectively considered as a single organ), representative of all lesions involved should be identified as TL at baseline. TLs should be selected on the basis of their size (longest diameter for non-nodal lesions or short axis diameter for nodal lesions), but in addition should be those that lend themselves to reproducible repeated measurements. It may be the case that, on occasion, the largest lesion does not lend itself to reproducible measurement in which circumstance the next largest lesion, which can be measured reproducibly, should be selected.

The site and location of each TL should be documented as well as the longest diameter for non-nodal lesions (or short axis for lymph nodes). All measurements should be recorded in millimetres. At baseline the sum of the diameters for all TL will be calculated and reported as the baseline sum of diameters. At follow-up visits the sum of diameters for all TL will be calculated and reported as the follow-up sum of diameters.

Special cases:

- For TL measurable in 2 or 3 dimensions, always report the longest diameter. For pathological lymph nodes measurable in 2 or 3 dimensions, always report the short axis diameter.
- If the CT/MRI slice thickness used is >5 mm, the minimum size of measurable disease at baseline should be twice the slice thickness of the baseline scan.
- If a lesion has completely disappeared, the diameter should be recorded as 0 mm. If a lesion appears in the same location on a subsequent scan, it will be recorded as a NL.
- If a TL splits into 2 or more parts, then record the sum of the diameters of those parts.

- If 2 or more TLs merge then the sum of the diameters of the combined lesion should be recorded for one of the lesions and 0 mm recorded for the other lesion(s).
- If a TL is believed to be present and is faintly seen but too small to measure, a default value of 5 mm should be assigned. If an accurate measure can be given, this should be recorded, even if it is below 5 mm.
- If a TL cannot be measured accurately due to it being too large, provide an estimate of the size of the lesion.
- When a TL has had any intervention eg, definitive radiotherapy, embolization, surgery, etc, during the study, the size of the TL should still be provided where possible and the intervention recorded in the RECIST 1.1 CRF. If a TL has been completely removed (surgery), the longest diameter should be recorded as 0 mm.

Evaluation of target lesions

This section provides the definitions of the criteria used to determine objective tumour visit response for TL (see [Table 15](#)).

Table 15 Evaluation of target lesions

| | |
|-----------------------------|--|
| Complete response (CR) | Disappearance of all TLs since baseline. Any pathological lymph nodes selected as TLs must have a reduction in short axis diameter to <10 mm. |
| Partial response (PR) | At least a 30% decrease in the sum of the diameters of TL, taking as reference the baseline sum of diameters. |
| Stable disease (SD) | Neither sufficient decrease in sum of diameters to qualify for PR nor sufficient increase to qualify for PD. |
| Progression of disease (PD) | At least a 20% increase in the sum of diameters of TLs, taking as reference the smallest previous sum of diameters (nadir) – this includes the baseline sum if that is the smallest on study. In addition to the relative increase of 20%, the sum must also demonstrate an absolute increase of at least 5 mm from nadir. |
| Not evaluable (NE) | Only relevant if any of the TLs at follow-up were not assessed or NE (eg, missing anatomy) or had a lesion intervention at this visit. Note: if the sum of diameters meets the PD criteria, PD overrides NE as a TL response. |

TL: Target lesion.

Non-target lesions

Evaluation of non-target lesions

All other lesions (or sites of disease) not recorded as TL should be identified as NTL at baseline. Measurements are not required for these lesions, but their status should be followed at subsequent visits. At each visit an overall assessment of the NTL response should be recorded by the Investigator. This section provides the definitions of the criteria used to

determine and record overall response for NTL at the investigational study site at each visit (see [Table 16](#)).

Table 16 Evaluation of non-target lesions

| | |
|-----------------------------|---|
| Complete response (CR) | Disappearance of all NTLs since baseline. All lymph nodes must be non-pathological in size (<10 mm short axis). |
| Non-CR/non-PD | Persistence of 1 or more NTL. |
| Progression of disease (PD) | Unequivocal progression of existing NTLs. Unequivocal progression may be due to an important progression in 1 lesion only or in several lesions. In all cases the progression MUST be clinically significant for the physician to consider changing (or stopping) therapy. |
| Not evaluable (NE) | Only relevant when 1 or some of the NTLs were not assessed and, in the Investigator’s opinion, they are not able to provide an evaluable overall NTL assessment at this visit. Note: for patients without TLs at baseline, this is relevant if any of the NTLs were not assessed at this visit and the progression criteria have not been met. |

NTL: Non-target lesion; TL: Target lesion.

To achieve ‘unequivocal progression’ on the basis of NTLs, there must be an overall level of substantial worsening in non-target disease such that, even in presence of SD or PR in TLs, the overall tumour burden has increased sufficiently to merit discontinuation of therapy. A modest ‘increase’ in the size of 1 or more NTLs is usually not sufficient to qualify for unequivocal progression status.

New lesions

Details of any NLs will also be recorded with the date of assessment. The presence of 1 or more NLs is assessed as progression. The finding of a NL should be unequivocal, ie, not attributable to differences in scanning technique, change in imaging modality or findings thought to represent something other than tumour. If a NL is equivocal, for example because of its small size, the treatment and tumour assessments should be continued until the previously NL has been assessed as unequivocal and then the progression date should be declared using the date of the initial scan when the NL first appeared.

A lesion identified at a follow-up assessment in an anatomical location that was not scanned at baseline is considered a NL and will indicate disease progression.

Symptomatic deterioration

Symptomatic (clinical) deterioration is not a descriptor of an objective response: it is a reason for stopping study therapy.

Patients with ‘symptomatic deterioration’ requiring discontinuation of treatment without objective radiologic evidence of disease progression at that time should continue to undergo tumour assessments where clinically feasible.

Evaluation of overall visit response

The overall visit response will be derived using the algorithm shown in [Table 17](#).

Table 17 Overall visit response

| Target lesions | Non-target lesions | New lesions | Overall response |
|----------------|--------------------|-------------|------------------|
| CR | CR | No | CR |
| CR | NA | No | CR |
| CR | Non-CR/Non-PD | No | PR |
| CR | NE | No | PR |
| PR | Non-PD or NE | No | PR |
| SD | Non-PD or NE | No | SD |
| NE | Non-PD or NE | No | NE |
| PD | Any | Yes or No | PD |
| Any | PD | Yes or No | PD |
| Any | Any | Yes | PD |

CR: Complete response; NA: Not applicable (only relevant if there were no target and/or NTLs at baseline); NE: Not evaluable; NTL: Non-target lesion; PD: Progression of disease; PR: Partial response; SD: Stable disease.

Confirmation of radiological progression

A follow-up scan is performed after the initial RECIST 1.1-defined PD, preferably at the next (and no later than the next) scheduled imaging visit, and no less than 4 weeks after the prior assessment of PD, and the Confirmation of Radiological Progression Criteria described below are applied for tumour assessments of this follow-up scan. Patients with confirmed radiological PD who continue to receive study drug at the discretion of the Investigator and patient (following consultation with AstraZeneca) can receive treatment until no longer having clinical benefit and will continue to have tumour assessments on their regular imaging schedule for the duration of treatment.

Confirmation of radiological progression guidelines are set for the following reasons:

- For patient management and treatment decisions.
- In the absence of significant clinical deterioration, to promote the collection of additional scans after the first radiologic RECIST 1.1 assessment of PD in order to distinguish pseudoprogression from true radiologic progression.

Confirmation of Radiological Progression Criteria

An immediate prior RECIST 1.1-defined radiologic PD would be considered confirmed if any of the following criteria are met in the subsequent follow-up scan (acquired preferably at the next regularly scheduled imaging visit but no sooner than 4 weeks after the RECIST 1.1-defined PD scan):

- $\geq 20\%$ increase in the sum diameters of TLs compared with the nadir at 2 consecutive visits, each with an absolute increase of at least 5 mm in sum of diameters compared to nadir (as per RECIST 1.1 definition);
- *and/or* significant progression (worsening) of NTLs at the follow-up scan timepoint compared with the immediate prior timepoint (as per RECIST 1.1 definition);
- *and/or* significant progression (worsening) of pre-existing NLs at the follow-up scan timepoint compared with the immediate prior timepoint (unique definition);
- *and/or* additional (brand) new unequivocal lesions at the follow-up scan timepoint (as per RECIST 1.1 definition).

NOTE: In order to have confirmed radiological progression, there should be 2 consecutive assessments meeting the PD definition: the first PD by RECIST 1.1 and the second PD using the Confirmation of Radiological Progression Criteria (above). If the first assessment fulfilling the PD definition by RECIST 1.1 is not confirmed, in the absence of significant clinical deterioration, then the patient may continue with assessments until the next PD by RECIST 1.1, which will also require a follow-up scan evaluated using the Confirmation of Radiological Progression Criteria. **If the first PD (by RECIST 1.1) is not confirmed by the immediate next scan, then the Investigator should not change the PD assessment of the first scan.**

Specifications for anatomical imaging

These notes are recommendations for use in clinical studies. The use of standardized protocols for CT and MRI allows comparability both within and between different studies, irrespective of where the examination has been undertaken.

CT scan

CT scans of the chest and abdomen (and pelvis when indicated) should be contiguous throughout all the anatomic region of interest.

The most critical CT image acquisition parameters for optimal tumour evaluation using RECIST 1.1 are *anatomic coverage, contrast administration, slice thickness, and reconstruction interval*.

a. Anatomic coverage: Optimal anatomic coverage for most solid tumours is the chest, abdomen and pelvis. Coverage should encompass all areas of known predilection for

metastases in the disease under evaluation and should additionally investigate areas that may be involved based on signs and symptoms of individual patients. Because a lesion later identified in a body part not scanned at baseline would be considered as a new lesion representing disease progression, careful consideration should be given to the extent of imaging coverage at baseline and at subsequent follow-up timepoints. This will enable better consistency not only of tumour measurements but also identification of new disease.

b. IV contrast administration: Optimal visualization and measurement of metastases in solid tumours requires consistent administration (dose and rate) of IV contrast as well as timing of scanning. Typically, most abdominal imaging is performed during the portal venous phase and (optimally) about the same time frame after injection on each examination. An adequate volume of a suitable contrast agent should be given so that the metastases are demonstrated to best effect and a consistent method is used on subsequent examinations for any given patient. It is very important that the same technique be used at Baseline and on follow-up examinations for a given patient. For patients who develop contraindications to contrast after baseline contrast CT is done, the decision as to whether non-contrast CT or MRI (enhanced or non-enhanced) should be performed should also be based on the tumour type, anatomic location of the disease and should be optimised to allow for comparison to the prior studies if possible. Each case should be discussed with the radiologist to determine if substitution of these other approaches is possible and, if not, the patient should be considered NE from that point forward. Care must be taken in measurement of TLs on a different modality and interpretation of non-target disease or NLs, since the same lesion may appear to have a different size using a new modality. Oral contrast is recommended to help visualize and differentiate structures in the abdomen.

If iodine contrast media is medically contraindicated at baseline or at any time during the course of the study, then the recommended methods are: CT thoracic (chest) examination without contrast and abdominal (and pelvis) MRI with contrast. If MRI cannot be performed, then CT without IV contrast is an option for the thorax and abdomen (and pelvis) examination. For brain imaging, MRI with IV contrast is the preferred method.

c. Slice thickness and reconstruction interval: It is recommended that CT scans be performed at 5 mm contiguous slice thickness and this guideline presumes a maximum 5 mm thickness in recommendations for measurable lesion definition. Exceptionally, particular institutions may perform medically acceptable scans at slice thicknesses greater than 5 mm. If this occurs, the minimum size of measurable lesions at Baseline should be twice the slice thickness of the baseline scans.

All window settings should be included in the assessment, particularly in the thorax where lung and soft tissue windows should be considered. When measuring lesions, the TL should be measured on the same window setting for repeated examinations throughout the study. All

images from each examination should be included in the assessment and not “selected” images of the apparent lesion.

MRI scan

MRI has excellent contrast, spatial and temporal resolution; however, there are many image acquisition variables involved in MRI, which greatly impact image quality, lesion conspicuity and measurement. Furthermore, the availability of MRI is variable globally. The modality used at follow-up should be the same as was used at baseline and the lesions should be measured/assessed on the same pulse sequence. Generally, axial imaging of the abdomen and pelvis (and other anatomies [eg, neck]) with T1 and T2 weighted imaging along with gadolinium-enhanced imaging can be performed. The field of view, matrix, number of excitations, phase encoding steps, use of fat suppression and fast sequences should be optimised for the specific body part being imaged as well as the scanner utilised. CT of the chest is typically recommended over MRI due to significant motion artefacts (heart, major blood vessels, breathing) associated with MRI. It is beyond the scope of this appendix to prescribe specific MRI pulse sequence parameters for all scanners, body parts and diseases. Ideally, the same type of scanner should be used, and the image acquisition protocol should be followed as closely as possible to prior scans. Body scans should be performed with breath-hold scanning techniques if possible.

[figure not shown]
For these reasons, CT is the imaging modality of choice.

References

Eisenhauer et al 2009

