- Notify the AstraZeneca representative
- Request a repeat of the test (new blood draw) by the central laboratory
- Complete the appropriate unscheduled laboratory CRF module(s) with the original local laboratory test result

When the identification criteria are met from central or local laboratory results the Investigator will without delay:

- Determine whether the patient meets PHL criteria (see [Appendix E, E 2](#) for definition) by reviewing laboratory reports from all previous visits (including both central and local laboratory results)

The Investigator will without delay review each new laboratory report and if the identification criteria are met will:

- Notify the AstraZeneca representative
- Determine whether the patient meets PHL criteria (see [Appendix E, E 2](#) for definition) by reviewing laboratory reports from all previous visits
- Promptly enter the laboratory data into the laboratory CRF

E 4 Follow-up

E 4.1 Potential Hy's law criteria not met

If the patient does not meet PHL criteria the Investigator will:

- Perform follow-up on subsequent laboratory results according to the guidance provided in the CSP.

E 4.2 Potential Hy's law criteria met

If the patient does meet PHL criteria the Investigator will:

- Notify the AstraZeneca representative who will then inform the central Study Team

The Study Physician contacts the Investigator, to provide guidance, discuss and agree an approach for the study patients' follow-up and the continuous review of data. Subsequent to this contact the Investigator will:

- Monitor the patient until liver biochemistry parameters and appropriate clinical symptoms and signs return to normal or baseline levels, or as long as medically indicated.
- Investigate the aetiology of the event and perform diagnostic investigations as discussed with the Study Physician.
- Complete the 3 Liver CRF Modules as information becomes available.
- If at any time (in consultation with the Study Physician) the PHL case meets serious criteria, report it as an SAE using standard reporting procedures.

E 5 Review and assessment of potential Hy's law cases

The instructions in this Section should be followed for all cases where PHL criteria are met.

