At the first on-study drug occurrence of PHL criteria being met, the Investigator will determine if there has been a significant change in the patients’ condition[#] compared with the last visit where PHL criteria were met.[#]

- If there is no significant change, no action is required.
- If there is a significant change, notify the AstraZeneca representative, who will inform the central Study Team, then follow the subsequent process described in [Appendix E, E 5](#).
- # A ‘significant’ change in the patient’s condition refers to a clinically relevant change in any of the individual liver biochemistry parameters (ALT, AST or TBL) in isolation or in combination, or a clinically relevant change in associated symptoms. The determination of whether there has been a significant change will be at the discretion of the Investigator, this may be in consultation with the Study Physician if there is any uncertainty.

E 7 Actions required for repeat episodes of potential Hy’s law

This section is applicable when a patient meets PHL criteria on study drug, and has already met PHL criteria at a previous on-study treatment visit.

The requirement to conduct follow-up, review, and assessment of a repeat occurrence(s) of PHL is based on the nature of the alternative cause identified for the previous occurrence.

The Investigator should determine the cause for the previous occurrence of PHL criteria being met and answer the following question:

Was the alternative cause for the previous occurrence of PHL criteria being met found to be the disease under study (eg, chronic or progressing malignant disease, severe infection or liver disease), or did the patient meet PHL criteria prior to starting study drug and at first on-study treatment visit, as described in [Appendix E, E 6](#).

If **No**: Follow the process described in [Appendix E, E 4.1](#).

If **Yes**: Determine if there has been a significant[#] change in the patient's condition compared with when PHL criteria were previously met.

If there is no significant change, no action is required.

If there is a significant change, follow the process described in [Appendix E, E 4](#).

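### Protocol Appendix E 7 sends repeat potential Hy's law cases on its 'No' branch to E 4.1 (criteria not met) instead of E 4.2 (criteria met)

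*Protocol*

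**What the plan says.** Protocol Appendix E sets out what an investigator does when liver tests rise. E 2 defines PHL as AST or ALT at least 3 times the upper limit of normal together with total bilirubin at least 2 times that limit. E 4 then splits by whether those criteria are met.

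- E 4.1 opens with "If the patient does not meet PHL criteria the Investigator will" and gives one instruction: "Perform follow-up on subsequent laboratory results according to the guidance provided in the CSP".
- E 4.2 opens with "If the patient does meet PHL criteria the Investigator will". It requires notification of the sponsor's representative, a follow-up approach agreed with the Study Physician, and monitoring until values and symptoms return to normal or baseline, or for as long as medically indicated. It also requires "Investigate the aetiology of the event and perform diagnostic investigations as discussed with the Study Physician" and "Complete the 3 Liver CRF Modules as information becomes available", and an SAE report if the case becomes serious.

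E 7 deals with repeat episodes. Its scope is stated as "This section is applicable when a patient meets PHL criteria on study drug, and has already met PHL criteria" at a previous on-treatment visit. It asks whether the earlier episode was explained by the disease under study, or whether the patient had already met PHL criteria before starting study drug (the E 6 situation). The two answers lead to different places:

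- No: "If No: Follow the process described in [Appendix E, E 4.1".
- Yes: no action is needed unless the patient's condition has changed significantly. Otherwise, "If there is a significant change, follow the process described in" E 4.

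**The concern.** E 7 sends a patient who meets PHL criteria to the section written for patients who do not. The 'No' answer also marks the patients for whom the reference matters most. Their earlier episode was not attributed to the disease or to a pre-treatment abnormality, so this group includes anyone whose earlier episode was attributed to the drug. Taken literally, they would get routine laboratory follow-up. A 'Yes' patient with a significant change would get the fuller E 4.2 process.

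At stake is the conduct of a safety procedure. Sections 8.2.1 and 8.3.8 send investigators to Appendix E for these cases. Safety is the trial's primary objective, and hepatitis or raised transaminases is a listed durvalumab risk (Section 2.3.2.1). A site that follows the reference as printed could leave out the E 4.2 steps for a repeat case.

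**Working it through.** No arithmetic applies. The check traces the E 7 reference to its target and compares the entry conditions.

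| Place in Protocol Appendix E | Who it applies to | What it requires |
|---|---|---|
| E 7 | Meets PHL criteria on study drug, and met them at an earlier on-treatment visit | Branch on the cause of the earlier episode |
| E 7, 'No' | As above; earlier episode not explained by the disease or by pre-treatment PHL | Go to E 4.1 |
| E 7, 'Yes' with significant change | As above; earlier episode so explained | Go to E 4 |
| E 4.1 | Does not meet PHL criteria | Laboratory follow-up only |
| E 4.2 | Does meet PHL criteria | Notification, Study Physician contact, monitoring, aetiology work-up, 3 Liver CRF modules, SAE report if serious |

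1. Every patient in E 7 meets PHL criteria, by E 7's own scope.
2. E 4.1's condition is that PHL criteria are not met. No patient in E 7 can satisfy it.
3. E 4.2's condition is that PHL criteria are met. Every patient in E 7 satisfies it.
4. The 'No' branch therefore names the one part of E 4 that can never apply.
5. The 'Yes, significant change' branch names E 4 as a whole. For a patient who meets PHL criteria this resolves to E 4.2, so that branch is correct.
6. Nothing else in the protocol or SAP redirects the 'No' branch. The version history does not mention Appendix E, so this is current text.

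The next question is which E 4.2 steps another provision already secures.

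- Sponsor notification: also required by E 3 once the identification criteria are met.
- Joint review with the Study Physician: E 5 covers every case meeting PHL criteria, with contact no later than 3 weeks after detection.
- SAE reporting: E 5 requires a report where the drug is the only explanation. It also requires one by default, with causality set to related, if the necessary information is delayed beyond 3 weeks. Section 8.2.1 separately requires an SAE report if the case meets Hy's law criteria after evaluation or a liver test meets a seriousness criterion.
- Search for other causes: E 5 cannot settle Hy's law status without one, and Section 8.4.5.1 asks for alternative causes of an immune-mediated event to be ruled out.
- The 3 Liver CRF modules, the follow-up agreed with the Study Physician and monitoring to normal or baseline: within Appendix E these are spelled out only in E 4.2.

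For the analysis, SAP Section 4.5.4.1 summarises, lists, plots and narrates these cases from laboratory values, so none of those outputs depends on the E 7 reference.

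**The case against.** The strongest reply is that nothing is lost. E 4.2 is not reached only through E 7. Its own opening condition is that the patient meets PHL criteria, with no limit to first episodes. An investigator who turns to E 4.1 finds that it does not fit and sees E 4.2 directly after it. The intent can also be recovered from E 7, where the only stated exemption from action is 'Yes' with no significant change. A rule giving 'No' patients less follow-up than 'Yes' patients with a change would make no sense, so many readers would recognise the slip. E 5 is a further backstop, because missing information leads to a default SAE report.

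Most of this stands. A reader might infer that E 4.2 is bypassed on this branch, or that repeat cases would go unreviewed or unreported. The documents do not support that: E 3, E 4.2 and E 5 are each triggered by the laboratory findings or by PHL status, whatever E 7 says. E 4.2 is contradicted by E 7 but remains in force. Appendix E also says it is not a comprehensive management guide and refers liver management to the toxicity guidelines, which are an annex not among the documents reviewed.

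The error itself remains. E 7 presents its own rule for how follow-up, review and assessment of a repeat episode are decided, so a site could reasonably treat the specific reference as controlling. An operative safety instruction should not depend on the investigator noticing that it contradicts the section it cites.

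**Conclusion.** The cross-reference is wrong, and this is certain from the text alone. It is a minor error in an operative safety instruction. It affects only repeat PHL cases answered 'No' in E 7. The documents give no frequency for these; they are probably few, but that is a judgement and not a figure from the plan.

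The realistic consequence is that a site following the reference literally could omit the follow-up agreed with the Study Physician, monitoring to normal or baseline, the aetiology work-up and the 3 Liver CRF modules. This assumes the site gives E 7's specific reference priority over E 4.2's general trigger. If it does not, nothing is lost. A reader might also infer some effect on the safety results. There is none to claim: no endpoint or planned analysis depends on this text.

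**What to change.** In the 'No' branch of Protocol Appendix E 7, change E 4.1 to E 4.2. Leave the 'Yes' branch as it is, since its reference to E 4 already resolves correctly.

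The cost is one corrected reference, with no change to visits, data collection or analysis. It can go into the next protocol amendment. If sites need to know sooner, Appendix A 5 already names letters to Investigators as a way to address safety issues.
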